In a between-subjects design, adult daily smokers (n=100) who are interested in trying e-cigarettes will be randomly assigned in 1:2:2 fashion to either a control group that receives no product (n=20), or to receive one of two types of e-cigarettes to sample over a three-week period: a) customizable tank, or b) pod, (n=40/group). The design is naturalistic in that participants receiving an e-cigarette will be told to use the e-cigarette as much or as little as they would like, allowing for assessment of self-determined uptake and reinforcement. Methods include both ecological assessments (electronic daily diaries) and experimental sessions (choice and purchase tasks). Biomarkers (expired carbon monoxide) will corroborate self-reported indices of use.

**Primary Specific Aim:** to assess the impact of e-cigarette product type (customizable tanks vs. pods) on product satisfaction ratings and relative reinforcement value (choices to smoke vs. use product in choice task, hypothetical purchase task). We hypothesize that pods will produce greater satisfaction ratings and relative reinforcement value than the customizable tanks.

**Secondary Aim:** to assess the impact of e-cigarette product type on tobacco use patterns including cigarette smoking (cigarettes per day, expired breath carbon monoxide) and e-cigarette uptake (e-cigarette puffing episodes). We hypothesize that pod style e-cigarettes will produce greater reductions in cigarette smoking compared to customizable tanks and greater uptake of e-cigarettes. Secondary analyses will compare the impact of e-cigarette sampling (control vs. all e-cigarette groups) on smoking during the sampling period.

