## C5. Measures

**C5a. Screening Assessments:** Preliminary eligibility will be determined on the phone before participants are either consented electronically or invited for an in-person visit to provide consent. Alternatively, participants may complete a Redcap survey to determine initial eligibility. Participants will see a script that briefly explains the study. Consented participants will attend an in-person visit where they complete screening questionnaires related to demographics, tobacco use history, and expired carbon monoxide.

**C5a. Measures of Subjective Effects:** Subjective effects will be assessed using a modified version of the Cigarette Evaluation Questionnaire (mCEQ), which assesses product satisfaction, psychological reward, craving reduction, enjoyment of sensations in the respiratory tract, and aversion. First, participants will sample their usual brand cigarette to standardize time since last cigarette. Participants will then sample their assigned e-cigarette and e-liquid. Immediately after sampling, participants will complete the mCEQ.

**C5b. Measures of Relative Reinforcement:** Relative reinforcement will be assessed using a lab-based choice task, a well-validated measure of reinforcement value. After participants sample their assigned product, they will complete choice task in which over a period of 30-minutes and 10 trials, participants choose between taking two puffs of the e-cigarette, two puffs of their usual (own) brand cigarette, or abstaining from both. Participants in the control group will choose between their usual brand cigarette and abstaining. In this case, the task will measure the impact of device type on changes in the relative reinforcement value of smoking compared to using the e-cigarette. The primary outcome is the number of choices to smoke. A secondary measure of reinforcement value will be purchase tasks—hypothetical tasks in which participants estimate the intensity with which they would use cigarettes and e-cigarettes at a variety of prices. The purchase tasks can be used to calculate several demand parameters, which are estimates of reinforcement value. Additional dependence measures will be included. [name] is utilizing these measures in recently completed and upcoming projects.

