## C6. Statistical Analysis, Power, and Predicted Outcomes

**C6a. Statistical Analysis:** We focus on changes in reinforcement value of cigarettes because the public health impact of e-cigarettes will be driven by changes in the use of cigarettes, rather than any direct effects of e-cigarettes. Our primary outcome is the percentage of choices for each participant to smoke the conventional cigarette during the choice task at Week 3 (ranging from 0 to 100%). A one-way ANOVA model will be used to compare the e-cigarette groups, while excluding the control group, to examine the effect of e-cigarette type. If there is no significant difference between e-cigarette types, e-cigarette participants will be combined and compared to the control group via a t-test to examine the effect of e-cigarette sampling. Other outcomes will be analyzed using general linear mixed models (GLMMs) controlling for baseline values and repeated measurements per participant will be used to examine group, time, and group by time interactions. Our secondary aim focuses on the average number of cigarettes smoked per day during Week 3 while also examining average e-cigarette puffing episodes, expired carbon monoxide. These outcomes will be examined in a similar manner via GLMMs. We will also conduct exploratory analyses to determine whether the effect of e-cigarette type or e-cigarette sampling depended on individual characteristics such as age, gender, race, and motivation to quit. Given the innovative and exploratory nature of this trial, there are no existing datasets that directly apply for the purposes of conducting a power calculation. However, a sample size of 30 per e-cigarette group will provide 80% power to detect moderate between-group differences in a one-way ANOVA comparing the primary outcome with a two-sided alpha=0.05.

**C7c. Predicted Outcomes:** We hypothesize that the pod e-cigarette will result in further reductions in choices to smoke during the choice task and in cigarette smoking (Figure 2).

**C8. Future Directions:** The goal of the proposed application is to gain preliminary data on the impact of e-cigarette type. An R01 grant application will follow the proposed project and will include a longer sampling period, longer follow up period, a more thorough investigation of the health effects of e-cigarette types, and a full investigation of any critical moderators (e.g., age).

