#### 1.2 Study Procedures, Materials, and Potential Risks:

##### Study Procedures:

Participants will be screened over the phone to determine initial eligibility. Alternatively, participants may complete a redcap survey to determine initial eligibility. Participants will see a script that briefly explains the study. Once participants have been determined to be initially eligible, they will be invited to participate in the consent process. The consent process will take place via one of the following modalities: 1) Remote electronic consent (e-consent) via REDCap facilitated with a discussion over the phone, 2) Remote consent via doxy.me, or 3) in-person consent (in-person visit at start of Visit 1). We have built in the option for electronic consent to reduce the length of the first in-person visit and while still providing ample time for the consent process. Consented participants will be asked to attend an in-person screening session. We will provide transportation via a taxi cab company (Yellow Cab) for participants who are eligible, but do not have reliable transportation to in-person visits. We will pay the cab company directly, the participant will not need to contribute. Participants will be asked to provide a carbon monoxide sample to confirm smoking status, and women will provide a urine sample for pregnancy testing. Participants will then complete a series of interview-administered and participant-administered questionnaires that assess brief medical history, tobacco use history including prior and current e-cigarette and cigarette use, current use of smoking cessation products, and demographics. After all questionnaires have been completed, study staff will determine participant eligibility.

Participants who are eligible will then complete additional baseline questionnaires including measures of nicotine dependence. Participants will be randomized as described above and will have the opportunity to sample their usual brand cigarette and their assigned e-cigarette and e-liquid for the first time. After sampling each product, participants will complete additional questionnaires and complete the preference assessment where they choose between their cigarette and assigned e-cigarette. At the end of Visit 1, participants will receive a three-week supply of e-liquid to take home with their assigned e-cigarette, will be enrolled in the daily electronic diary system, and will be provided with instructions for completing diaries.

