Participants will complete weekly phone calls after one and two weeks of sampling and will return to the lab for an in-person visit after three weeks of sampling. At each visit or phone call, we will assess tobacco use during the prior week, adverse events will be assessed, and participants will complete questionnaires about their assigned e-cigarette and e-liquid. At each in-person visit, participants will provide an expired breath carbon monoxide sample. At the fourth and final weekly visit, participants will complete the sampling and preference assessment again, and return any unused study product.

**Modified Procedures to be Implemented During COVID-19 Restrictions:** After passing initial screening, all participants will be consented into the study through our established remote procedures, instead of having the option to complete the consent process in person. All in-person screening questionnaires that can be administered over the phone prior to the visit will be completed over the phone (demographics questionnaire, physiological & medical history, & tobacco use history). Participants who are ineligible based on these questionnaires will be paid for the visit, but not required to come in to the lab to complete the remaining screening assessments. If the participant is still eligible after completing these questionnaires, we will then schedule them to come into the laboratory to complete the remainder of the visit. For visit 2, we will complete any questionnaires remotely that we can be completed remotely. For interview-administered questionnaires, we will call participants in advance of the visit and complete the questionnaire over the phone via interview with study staff. For questionnaires that are completed independently by the participant, we will send them a RedCAP link prior to the visit and request that they complete the questionnaires on their own. If participants fail to complete these questionnaires on their own or we are unable to reach them to complete the questionnaires, we will ask the participant to complete them at the visit in the lab.

Participants will be called 24 hours prior to all visits to confirm they are not experiencing any symptoms of COVID-19. All participants for each visit will be required to wear a mask and remain six feet away from the research staff

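### Does controlling for baseline remove part of the device effect on satisfaction, given that the assigned device is first rated after randomisation?

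*Combined protocol and SAP*

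**What the plan says.** The named primary outcome is the percentage of choices to smoke at Week 3, compared between the two device groups by one-way ANOVA with no covariate stated (C6a). For the rest, C6a says: "Other outcomes will be analyzed using general linear mixed models (GLMMs) controlling for baseline values and repeated measurements per participant". It then lists group, time and their interaction as the terms to be examined. It does not say what baseline means for each outcome, or which term tests device type.

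The Primary Specific Aim is "to assess the impact of e-cigarette product type (customizable tanks vs. pods) on product satisfaction ratings and relative reinforcement value", so satisfaction is part of it. No time point is attached to satisfaction there.

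The section on subjective effects in C5 ties the mCEQ to laboratory sampling: "Participants will then sample their assigned e-cigarette and e-liquid. Immediately after sampling, participants will complete the mCEQ". Section 1.2 (Study Procedures) gives the order at Visit 1. Before randomisation, "Participants who are eligible will then complete additional baseline questionnaires including measures of nicotine dependence". After that, "Participants will be randomized as described above and will have the opportunity to sample their usual brand cigarette and their assigned e-cigarette", and this is the first use of the device. Sampling is repeated at the final visit (C1 and section 1.2). At each visit or call "participants will complete questionnaires about their assigned e-cigarette and e-liquid", but the mCEQ is not named there.

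**The concern.** A rating of the assigned device cannot exist before the device has been assigned and tried. Read literally, the rule in C6a therefore offers two options for satisfaction: no same-measure covariate, or the Visit 1 rating, which the device may already have influenced. Adjusting for the latter conditions on a post-randomisation value and takes out whatever part of the device effect was already present at first use.

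That matters because the protocol expects pods to be more satisfying, and section A3 attributes this partly to features a participant would notice at once, such as throat hit and ease of use. An early gap is therefore plausible. The reported Week 3 effect could then depend on a choice of covariate made after the data are in. Any e-cigarette purchase task first completed after sampling would raise the same question.

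**Working it through.** **The plan's own figure.** C6a claims 80% power with 30 per e-cigarette group for moderate differences on the primary outcome (two-sided alpha 0.05). With 30 per group, a two-group comparison reaches 80% at a standardised difference of 0.74. C6a puts no number on moderate, so the claim can be neither confirmed nor refuted. It concerns a different outcome and does not enter below.

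**Inputs.** From the documents: 40 per device group (Specific Aims, C1) and two-sided alpha 0.05 (C6a). Assumed, because the documents give none of them: SD 1 at both visits, complete data, d3 = 0.5 SD, d1 equal to d3, half of d3 or zero, and r = 0.3, 0.5 or 0.7.

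**Formulas.** With the Visit 1 rating as covariate:

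- coefficient = d3 − r·d1
- SE = √[(1 − r²)(2/n + d1²/(2(n − 1)))], with 2n − 3 degrees of freedom

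Example with d1 = d3 = 0.5 and r = 0.5: the coefficient is 0.5 − 0.25 = 0.25, and SE = √[0.75 × (0.05 + 0.25/78)] = 0.200. The ratio is 1.25 and power from the noncentral t is 23.5%. Without the covariate, SE = √(2/40) = 0.224, the ratio is 2.24 and power is 59.8%.

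| d1 | Estimate at r = 0.3 / 0.5 / 0.7 | Power with Visit 1 covariate | Power without |
|---|---|---|---|
| 0.5 | 0.35 / 0.25 / 0.15 | 35% / 24% / 15% | 60% |
| 0.25 | 0.425 / 0.375 / 0.325 | 50% / 48% / 51% | 60% |
| 0 | 0.50 / 0.50 / 0.50 | 64% / 72% / 87% | 60% |

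Simulation (20,000 replicates) agrees with the estimates to within about 0.002 SD and with the power figures to within about 1 percentage point. Adjustment costs power once d1/d3 exceeds about (1 − √(1 − r²))/r = 0.15 / 0.27 / 0.41. If d1 had the opposite sign, the estimate would be inflated: d1 = −0.25 with r = 0.5 gives 0.5 + 0.125 = 0.625. The direction of any net harm is therefore not fixed.

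**Which reading does the plan support?**

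1. *Use of the word.* C2 applies baseline to the carbon monoxide entry criterion, and section 1.2 applies it to questionnaires completed before randomisation. On that usage, the Visit 1 device rating is not a baseline value. The covariate is simply unavailable for this outcome, and no attenuation arises.
2. *Structure of the model.* C6a calls for repeated measurements with time and group-by-time terms. The mCEQ is expressly placed at two samplings, Visit 1 and the final visit. If Visit 1 becomes a covariate, one response per participant remains and neither time term can be estimated. With both visits as responses, the model can be fitted as written and the device contrast at either visit is intact.

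**Which contrast?** With both visits as responses, the group term averaged over them estimates (d1 + d3)/2. If d1 = d3 its power is 79% / 72% / 67%, above the 60% of the Week 3 contrast. If d1 is half of d3 it estimates 0.375 SD with power 54% / 48% / 43%, below 60%. Neither is better throughout, and the Primary Specific Aim does not choose between them.

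**The case for a change.** The strongest reply is that C6a says none of this outright. The word is undefined, the rule is worded for all other outcomes, and satisfaction sits in the Primary Specific Aim with a directional hypothesis. If the questionnaires at the weekly calls include the mCEQ, Visit 1 could serve as covariate with later weeks as responses, and the time terms could then be fitted after all. The choice of term also matters: with Visit 1 as a response and d1 = d3, the interaction targets d3 − d1 = 0 and would reject only at the 5% alpha level, while the averaged group term has 67% to 79% power. The results are meant to inform a later grant application, and extra wording would be cheap.

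Part of this stands. The definition is missing, and the unnamed test term leaves an analyst some freedom. But the weekly mCEQ is a supposition, since C5 describes the questionnaire as completed immediately after laboratory sampling. The two options in the concern are also not exhaustive. The usual-brand cigarette is sampled before the device, with questionnaires after each product. If the mCEQ is among them, a usual-brand rating would precede device use, although it too is listed after randomisation and could be affected by knowledge of the assignment. Finally, insisting on Week 3 for satisfaction is a preference: first-use satisfaction and the average over visits are equally fair readings of the aim.

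**Conclusion.** The concern describes correctly what would happen if the Visit 1 device rating were used as a covariate, but the plan does not call for that. Its own use of baseline, and a model with time terms applied to an outcome expressly placed at two visits, both lead to Visit 1 as a response. Analysed that way, the device effect is not diluted. What remains is missing detail that a competent analyst would fill in the sound way, together with a choice between the Week 3 and visit-averaged contrasts that is a fair trade-off.

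The possible loss is not established. Under assumed inputs (d3 = 0.5 SD, 40 per group, r from 0.3 to 0.7), the covariate could lower power to 15% or raise it to 87%, against 60% without it, depending on a Visit 1 effect that the documents do not give. The reach is small: the primary outcome has no stated baseline covariate, cigarettes per day and carbon monoxide can have values from before device use, and the protocol presents the trial as preliminary. This conclusion rests on the mCEQ being given only at the two laboratory samplings, as C5 and section 1.2 indicate, and on baseline keeping its usual meaning. No change to the plan is needed.

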## Protection of Human Subjects

### 1. Risks to Human Subjects

#### 1.1 Human Subjects Involvement, Characteristics, and Design:

Current smokers will be randomly assigned in a 1:2:2 between-subjects design to either not receive an e-cigarette (control group, n=20) or to receive one of two e-cigarette types: a customizable tank, or pods (n=40/each). All participants will receive an e-cigarette and e-liquid to sample over a three-week period.

#### 1.2 Study Procedures, Materials, and Potential Risks:

##### Study Procedures:

Participants will be screened over the phone to determine initial eligibility. Alternatively, participants may complete a redcap survey to determine initial eligibility. Participants will see a script that briefly explains the study. Once participants have been determined to be initially eligible, they will be invited to participate in the consent process. The consent process will take place via one of the following modalities: 1) Remote electronic consent (e-consent) via REDCap facilitated with a discussion over the phone, 2) Remote consent via doxy.me, or 3) in-person consent (in-person visit at start of Visit 1). We have built in the option for electronic consent to reduce the length of the first in-person visit and while still providing ample time for the consent process. Consented participants will be asked to attend an in-person screening session. We will provide transportation via a taxi cab company (Yellow Cab) for participants who are eligible, but do not have reliable transportation to in-person visits. We will pay the cab company directly, the participant will not need to contribute. Participants will be asked to provide a carbon monoxide sample to confirm smoking status, and women will provide a urine sample for pregnancy testing. Participants will then complete a series of interview-administered and participant-administered questionnaires that assess brief medical history, tobacco use history including prior and current e-cigarette and cigarette use, current use of smoking cessation products, and demographics. After all questionnaires have been completed, study staff will determine participant eligibility.

Participants who are eligible will then complete additional baseline questionnaires including measures of nicotine dependence. Participants will be randomized as described above and will have the opportunity to sample their usual brand cigarette and their assigned e-cigarette and e-liquid for the first time. After sampling each product, participants will complete additional questionnaires and complete the preference assessment where they choose between their cigarette and assigned e-cigarette. At the end of Visit 1, participants will receive a three-week supply of e-liquid to take home with their assigned e-cigarette, will be enrolled in the daily electronic diary system, and will be provided with instructions for completing diaries.

Participants will complete weekly phone calls after one and two weeks of sampling and will return to the lab for an in-person visit after three weeks of sampling. At each visit or phone call, we will assess tobacco use during the prior week, adverse events will be assessed, and participants will complete questionnaires about their assigned e-cigarette and e-liquid. At each in-person visit, participants will provide an expired breath carbon monoxide sample. At the fourth and final weekly visit, participants will complete the sampling and preference assessment again, and return any unused study product.

**Modified Procedures to be Implemented During COVID-19 Restrictions:** After passing initial screening, all participants will be consented into the study through our established remote procedures, instead of having the option to complete the consent process in person. All in-person screening questionnaires that can be administered over the phone prior to the visit will be completed over the phone (demographics questionnaire, physiological & medical history, & tobacco use history). Participants who are ineligible based on these questionnaires will be paid for the visit, but not required to come in to the lab to complete the remaining screening assessments. If the participant is still eligible after completing these questionnaires, we will then schedule them to come into the laboratory to complete the remainder of the visit. For visit 2, we will complete any questionnaires remotely that we can be completed remotely. For interview-administered questionnaires, we will call participants in advance of the visit and complete the questionnaire over the phone via interview with study staff. For questionnaires that are completed independently by the participant, we will send them a RedCAP link prior to the visit and request that they complete the questionnaires on their own. If participants fail to complete these questionnaires on their own or we are unable to reach them to complete the questionnaires, we will ask the participant to complete them at the visit in the lab.

Participants will be called 24 hours prior to all visits to confirm they are not experiencing any symptoms of COVID-19. All participants for each visit will be required to wear a mask and remain six feet away from the research staff

and others when possible. When staff and participants must interact (for CO collection and e-cigarette disbursal), at least six feet of distance will be maintained by placing materials on a desk/table six feet away from the participant and then staff stepping away while the participant approaches to retrieve materials. All surfaces will be sanitized prior to the visit and after the visit.

